## **9.7.2 Part D**

Part D is a single cohort part; dose escalation criteria are not applicable.

## **9.8 Stopping Rules**

### **9.8.1 Parts A, B, and C**

#### **Stopping Rules for Cohorts**

In Parts A and B, dose escalation will be stopped if the mean  $AUC_{0-\infty}$  (single-dose escalation) or  $AUC_{0-24h}$  (multiple-dose escalation) of the next dose is predicted to exceed an AUC of 356  $\mu\text{g}\cdot\text{h}/\text{mL}$  or the  $C_{\max}$  is predicted to exceed 21  $\mu\text{g}/\text{mL}$  [REDACTED]

[REDACTED] Dose escalation will also consider individual subject exposure and potential outliers. Exposures in male and female rats were higher than the dog at the NOAEL in the rat 28-day GLP toxicity study.

If a serious adverse event (SAE) occurs that is considered related or possibly related to study drug, or if 2 severe (or greater) AEs occur that are considered related or possibly related to study drug, then the study will be halted (dosing of study drug in all study subjects will be halted). Occurrence of such events will trigger an internal safety review, including discussion between the investigator and medical monitor, and notification to regulatory authorities and ethics committees, if applicable. If the sponsor decides it is appropriate to restart the study, dosing of study drug will be resumed only after approval of a substantial amendment to the Clinical Trial Authorization.

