## **9.8.2 Part D**

The medical monitor should be notified of a discontinuation of study drug or an interruption of study drug that lasts >72 hours for any reason and of the resumption of study drug after such interruption.

Subjects with new treatment-emergent ALT or AST elevations of  $>3 \times \text{ULN}$ , or total bilirubin  $>2 \times \text{ULN}$ , must be followed closely, including confirmatory testing performed by the central laboratory within 48 to 72 hours of the initial finding and subsequent close monitoring of ALT, AST, and bilirubin levels, as clinically indicated.

If a subject cannot return to the site for confirmatory testing, a local laboratory may be used. Local laboratory results must be reported immediately to the medical monitor, and the subject must have the tests repeated and sent to the central laboratory as soon as possible (ideally within 48 to 72 hours).

Study drug administration **must be interrupted** immediately (prior to confirmatory testing) if any of the following criteria are met:

- ALT or AST  $>8 \times$  ULN
- ALT or AST  $>5 \times$  ULN for more than 2 weeks
- ALT or AST  $>3 \times$  ULN, in association with total bilirubin  $>2 \times$  ULN and/or clinical jaundice

A thorough investigation of potential causes should be conducted, and the subject should be followed closely for clinical progression.

Study drug administration **must be discontinued** if subsequent ALT or AST values confirm the initial elevation that satisfied the interruption rule (above), and no convincing alternative etiology (e.g., acetaminophen use, viral hepatitis, alcohol ingestion) is identified, regardless of whether transaminase levels have improved.

All subjects in whom treatment is discontinued for elevated transaminases and/or bilirubin should have these levels monitored closely until levels normalize or return to baseline.

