If an alternative, reversible cause of transaminase elevation and/or increased bilirubin or clinical jaundice has been identified, study drug administration may be resumed once transaminases or bilirubin return to baseline or are  $\leq 2 \times$  ULN, whichever is higher. Regardless of the duration of interruption, the medical monitor should be notified prior to resumption of study drug. Upon resumption of study drug, transaminases and bilirubin should be assessed weekly until the Safety Follow-up Visit. If a protocol-defined transaminase or bilirubin elevation interruption threshold recurs with rechallenge with the study drug (with confirmation of the initial elevation by repeat testing within 48 to 72 hours), then the study drug must be permanently discontinued, regardless of the presumed etiology.

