##### **13.1.1.2 Clinically Significant Assessments**

Study assessments including laboratory tests, ECGs, PEs, and vital signs will be assessed and those deemed to have clinically-significant worsening from baseline will be documented as an AE. When possible, a clinical diagnosis for the study assessment will be provided, rather than the abnormal test result alone (e.g., urinary tract infection, anemia). In the absence of a diagnosis, the abnormal study assessment itself will be listed as the AE (e.g., bacteria in urine or decreased hemoglobin).

An abnormal study assessment is considered clinically significant if the subject has 1 or more of the following:

- Concomitant signs or symptoms related to the abnormal study assessment
- Further diagnostic testing or medical/surgical intervention
- A change in the dose of study drug or discontinuation from the study

Repeat testing to determine whether the result is abnormal, in the absence of any of the above criteria, does not necessarily meet clinically significant criteria. The determination of whether the study assessment results are clinically significant will be made by the investigator.

A laboratory value that is Grade 4 will not automatically be an SAE. A Grade 4 laboratory value will be an SAE if the subject's clinical status indicates a life-threatening AE.

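### In the visible text only Part D has liver values that by themselves stop a subject's dosing; in re-dosed Cohorts A3 and A9 and in Parts B and C, stopping rests on judgement

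*Protocol*

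**What the plan says.** Protocol 9.8 divides the stopping rules by part.

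- **Part D (9.8.2).** New ALT or AST above 3 × ULN, or total bilirubin above 2 × ULN, "must be followed closely, including confirmatory testing performed by the central laboratory within 48 to 72 hours of the initial finding". Dosing must be interrupted "immediately (prior to confirmatory testing) if any of the following criteria are met": ALT or AST above 8 × ULN; above 5 × ULN for more than 2 weeks; or above 3 × ULN with total bilirubin above 2 × ULN and/or clinical jaundice. Discontinuation is mandatory if later values confirm the elevation "and no convincing alternative etiology (e.g., acetaminophen use, viral hepatitis, alcohol ingestion) is identified".
- **Parts A, B and C (9.8.1).** The visible text limits predicted AUC and Cmax (Parts A and B) and halts dosing in all subjects after one related or possibly related SAE, or "if 2 severe (or greater) AEs occur that are considered related or possibly related to study drug, then the study will be halted". Two blocks next to the exposure limits are redacted.
- **Other text that reaches Parts A to C.** Section 9.7.1 requires the investigator, medical monitor and sponsor safety physician to evaluate every Grade 3 or higher laboratory abnormality and decide whether dosing or escalation continues. Section 9.9 requires discontinuation for unacceptable toxicity without defining it. Section 9.8.3 asks for close monitoring of subjects with AEs. On whether a laboratory finding counts as an AE, 13.1.1.2 says "The determination of whether the study assessment results are clinically significant will be made by the investigator", and adds "A laboratory value that is Grade 4 will not automatically be an SAE".

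The SAP adds no stopping rule. Section 7.1 refers back to protocol 9.8.1, and the liver threshold tables (9.4.2, Appendix D) are for Part D summaries only.

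**The concern.** Safety and tolerability are the primary objective in every part, and healthy volunteers gain nothing from continued dosing. For Part D the sponsor has already fixed liver values at which the next dose may not be given. A volunteer in Part B or C with the same values has no such protection in the visible text, and whether the next dose is given is decided case by case. The same holds in Cohorts A3 and A9, which are dosed again after scheduled chemistry. At stake is whether one subject with a marked elevation could receive further doses while the finding is being assessed.

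**Working it through.** **1. Does any liver value by itself stop a subject's dosing?**

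| Route | Part D | Cohorts A3, A9, Parts B, C | What it needs outside Part D |
|---|---|---|---|
| Numeric individual rule | Yes, 9.8.2 | None visible | n/a |
| Grade 3+ review, 9.7.1 | Not stated | Yes | A decision; no outcome is fixed |
| Unacceptable toxicity, 9.9 | Yes | Yes | A judgement; no definition |
| Study halt, 9.8.1 | Not stated | Yes | Judgements of significance, of severity or seriousness, and of causality |

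Take one subject with ALT above 8 × ULN, recorded as a related, severe but non-serious AE, and the first such event. In Part D dosing stops before the repeat test. In Part B or C there is no SAE and only one severe AE, so neither limb of the halt is met and the outcome rests on the review.

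**2. Coverage**

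Inputs: cohorts of about 8 randomized 3:1 (Table 9-1); six Part B and two Part C cohorts (synopsis); 9 active subjects in Part D (Figure 9-1); 10, 14 and 29 dosing days (Tables 3-5, 3-6, 3-7).

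The plan's total reproduces: 7 × 8 + 6 × 8 + 2 × 8 + 12 = 132. Active per cohort: 8 × 3/4 = 6.

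- Active subjects on daily dosing: B 6 × 6 = 36; C 2 × 6 = 12; D 12 × 3/4 = 9. Share without a numeric rule: 48/57 = 84%.
- Active dosing-days: B 36 × 10 = 360; C 12 × 14 = 168; D 9 × 29 = 261. Share: 528/789 = 66.9%, or 528/780 = 67.7% if Part D is counted as 28 days.
- Only the four Part B dose levels labelled in SAP 9.1: 36/45 = 80% of subjects; 408/669 = 61% of days.
- All optional cohorts run (8 in B, 4 in C): 72/81 = 89% of subjects; 816/1077 = 76% of days.
- Adding the planned active single doses of Part A, 6 × 6 + 8 + 8 × 3 = 68, which also lack a numeric rule: (528 + 68)/(789 + 68) = 596/857 = 69.5%.

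**3. Is exposure higher where the rule is absent?**

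- Daily dose: B2, B3, B4 and C2, 24 of 48 active subjects (50%), have a named dose above the planned Part D dose of 10 mg. B1 and C1 (12) are at 10 mg. B5 and B6 (12) are to be determined.
- Cumulative dose: B1 100, B2 200, B3 400, B4 600, C1 140 and C2 280 mg, against 10 × 29 = 290 mg in Part D. Among the named doses only B3 and B4 exceed it: 12 of 48 (25%).

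**4. Would a rule have anything to act on?**

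| | Scheduled chemistry | Dosing still to come |
|---|---|---|
| Part B | Days 2, 5 | 8, 5 days |
| Part C | Days 2, 6, 10 | 12, 8, 4 days |
| A3 (doses Days 1, 9) | Day 2 | 1 dose |
| A9 (doses Days 1, 9, 17) | Days 2, 10 | 2, 1 doses |

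The documents give no laboratory turnaround time. The Part B and C counts assume the result is back before the next morning's dose. Part C also has an evening IVA dose on the day of the test.

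**The case against.** The existing controls are substantial. The Grade 3 or higher review is mandatory, ongoing and made by three parties against a named toxicity scale. Discontinuation for unacceptable toxicity is mandatory in every part. Two related severe AEs, or one related SAE, stop dosing in everyone, and restart needs a substantial amendment; 9.8.2 has no comparable halt. The settings also differ. Part D subjects are outpatients seen one to two weeks apart, and may enter with ALT or AST raised to just under 3 × ULN. Parts A to C enrol healthy subjects who stay in the unit and take every dose under supervision. This all stands, and it is why the gap is modest. It does not supply a value at which stopping is required: supervision makes stopping easy without saying when it must happen.

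Three stronger readings are tempting and are not supported.

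- A reader might infer that Parts A to C have no liver oversight. They do; what is missing is a fixed outcome.
- A reader might take 84% or 67% as a measure of risk. The documents give no probability of reaching these values, or of dosing continuing afterwards, and only 12 of 48 subjects have a named cumulative dose above Part D's.
- A reader might conclude that no individual rule was ever written. The redacted blocks sit among exposure text, which suggests exposure content but does not prove it.

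**Conclusion.** The point holds for the visible text. Mandatory numeric liver values for an individual subject exist only in 9.8.2, for Part D. In Cohorts A3 and A9 and in Parts B and C, no ALT, AST or bilirubin value by itself stops dosing. Coverage is large on paper but the practical gap is modest. The reason to act is that a rule the sponsor already uses in this protocol would remove the remaining discretion at low cost.

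The conclusion assumes that no liver rule lies in the redacted part of 9.8.1; if one does, the sponsor can close the point by saying so. The counts assume the planned cohorts and full dosing. Confidence is medium, because of the redaction.

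**What to change.** Add to 9.8.1 an individual-subject rule for Cohorts A3 and A9 and Parts B and C. State that it is additional to the 9.7.1 review and does not limit earlier stopping. The documents do not give the toxicity scale's ALT cut-offs, so 8 × ULN must not be read as a tolerance limit.

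- (a) New ALT or AST above 3 × ULN, or total bilirubin above 2 × ULN: prompt repeat at the local laboratory and close monitoring.
- (b) ALT or AST above 8 × ULN, or above 3 × ULN with total bilirubin above 2 × ULN and/or clinical jaundice: withhold all further study drug at once, including the Part C evening IVA dose, before the repeat test.
- (c) If the elevation is confirmed and no convincing alternative cause is found: discontinue that subject's dosing and monitor until values normalise or return to baseline.

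Part D's resumption pathway ("study drug administration may be resumed once transaminases or bilirubin return to baseline") need not be carried over. It has little use in 10 to 14 days, and volunteers gain nothing from rechallenge. Allow a restart only after a documented laboratory error, with the medical monitor notified. The value of 5 × ULN for more than 2 weeks can be left out, because it cannot operate within Part B or C dosing. In A9 it could reach only the Day 17 dose (Day 2 to Day 17 is 15 days).

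The cost is protocol wording and an occasional unscheduled repeat test, with no new scheduled sample. A few subjects may have incomplete steady-state PK, or an incomplete within-subject comparison in A3 or A9, and 9.10 provides on-treatment replacement only after nonsafety withdrawals. In Parts B and C a cohort of 8 with 6 active can lose 2 active subjects and still meet the 9.7.1 minimum: 8 − 2 = 6 subjects and 6 − 2 = 4 active.

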## **9.8.2 Part D**

The medical monitor should be notified of a discontinuation of study drug or an interruption of study drug that lasts >72 hours for any reason and of the resumption of study drug after such interruption.

Subjects with new treatment-emergent ALT or AST elevations of  $>3 \times \text{ULN}$ , or total bilirubin  $>2 \times \text{ULN}$ , must be followed closely, including confirmatory testing performed by the central laboratory within 48 to 72 hours of the initial finding and subsequent close monitoring of ALT, AST, and bilirubin levels, as clinically indicated.

If a subject cannot return to the site for confirmatory testing, a local laboratory may be used. Local laboratory results must be reported immediately to the medical monitor, and the subject must have the tests repeated and sent to the central laboratory as soon as possible (ideally within 48 to 72 hours).

Study drug administration **must be interrupted** immediately (prior to confirmatory testing) if any of the following criteria are met:

- ALT or AST  $>8 \times$  ULN
- ALT or AST  $>5 \times$  ULN for more than 2 weeks
- ALT or AST  $>3 \times$  ULN, in association with total bilirubin  $>2 \times$  ULN and/or clinical jaundice

A thorough investigation of potential causes should be conducted, and the subject should be followed closely for clinical progression.

Study drug administration **must be discontinued** if subsequent ALT or AST values confirm the initial elevation that satisfied the interruption rule (above), and no convincing alternative etiology (e.g., acetaminophen use, viral hepatitis, alcohol ingestion) is identified, regardless of whether transaminase levels have improved.

All subjects in whom treatment is discontinued for elevated transaminases and/or bilirubin should have these levels monitored closely until levels normalize or return to baseline.

If an alternative, reversible cause of transaminase elevation and/or increased bilirubin or clinical jaundice has been identified, study drug administration may be resumed once transaminases or bilirubin return to baseline or are  $\leq 2 \times$  ULN, whichever is higher. Regardless of the duration of interruption, the medical monitor should be notified prior to resumption of study drug. Upon resumption of study drug, transaminases and bilirubin should be assessed weekly until the Safety Follow-up Visit. If a protocol-defined transaminase or bilirubin elevation interruption threshold recurs with rechallenge with the study drug (with confirmation of the initial elevation by repeat testing within 48 to 72 hours), then the study drug must be permanently discontinued, regardless of the presumed etiology.

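### The recovery clause of the Part D restart rule does not require every raised liver test to recover, or clinical jaundice to resolve, before study drug is resumed

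*Protocol*

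**What the plan says.** Protocol 9.8.2 (Part D) stops dosing at once in any of three situations:

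- ALT or AST above 8×ULN;
- ALT or AST above 5×ULN for longer than 2 weeks;
- ALT or AST above 3×ULN "in association with total bilirubin" above 2×ULN and/or clinical jaundice (the joint trigger).

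New ALT or AST above 3×ULN, or total bilirubin above 2×ULN, "must be followed closely, including confirmatory testing performed by the central laboratory within 48 to 72 hours of the initial finding". After an interruption, "A thorough investigation of potential causes should be conducted". If the elevation is confirmed and no convincing other cause is found, the drug is stopped for good.

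The restart paragraph begins "If an alternative, reversible cause of transaminase elevation and/or increased bilirubin or clinical jaundice has been identified", and continues "study drug administration may be resumed once transaminases or bilirubin return to baseline or are" at or below 2×ULN, whichever limit is higher. Three safeguards follow:

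- Before restart there is a notice requirement: "Regardless of the duration of interruption, the medical monitor should be notified prior to resumption of study drug".
- After restart there is a testing requirement: "Upon resumption of study drug, transaminases and bilirubin should be assessed weekly until the Safety Follow-up Visit".
- Should an interruption threshold recur on rechallenge and be confirmed, "then the study drug must be permanently discontinued, regardless of the presumed etiology".

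Nothing else in the protocol or SAP says which analytes must have recovered. SAP Appendix D, Table 12-2 only counts joint elevations.

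**The concern.** Interruption limits of 8, 5 or 3×ULN and a restart limit of 2×ULN imply a deliberate gap: a subject should come well down before being re-exposed. The recovery clause does not secure that gap, because it joins the two analytes with a bare 'or'. The same section uses 'and' for the weekly tests and 'and/or' for the joint trigger, so the connectives are not otherwise interchangeable. Clinical jaundice can be part of the trigger and is named in the cause clause, but it is not in the recovery condition.

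This rule protects individual subjects in an outpatient, first-in-patient part of the study that has no IDMC. Two investigators could apply it differently: one waits for everything to recover, the other re-doses when one analyte has. ALT/AST of 4×ULN would have excluded the subject at screening under 8.2.2, and so would bilirubin of 2.5×ULN.

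**Working it through.** The plan gives no figure to reproduce. The check compares the restart clause with the interruption triggers.

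**Inputs.** A is the higher of ALT and AST, and B is total bilirubin, both in ×ULN. Triggers and restart limit come from Protocol 9.8.2. Protocol 8.2.2 excludes ALT or AST of 3×ULN or more, and total bilirubin of 2×ULN or more, at screening. The restart limit for A is the higher of baseline and 2×ULN. It is therefore 2×ULN for a baseline at or below 2×ULN and can approach 3×ULN, assuming baseline stays within the screening limit.

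**Rules, for baseline at or below 2×ULN.**
- Literal clause: A ≤ 2 or B ≤ 2.
- Proposed clause: A ≤ 2 and B ≤ 2, and jaundice that was part of the interruption has resolved.
- Dosing still barred: A > 8; or A > 5 for more than 2 weeks; or A > 3 with B > 2 and/or jaundice.

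**States after a joint trigger** (jaundice, where present, was part of the interruption):

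| A | B | Jaundice | Literal clause met | Trigger still met | Proposed clause met |
|---|---|---|---|---|---|
| 1.5 | 2.5 | yes | yes | no | no |
| 1.5 | 0.8 | yes | yes | no | no |
| 4 | 0.8 | no | yes | no | no |
| 6 | 0.8 | no | yes | no, if A > 5 has lasted 2 weeks or less | no |
| 4 | 0.8 | yes | yes | yes | no |
| 4 | 2.5 | no | no | yes | no |

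In the first four rows the text permits restart with a raised analyte or persisting jaundice. In the fifth the restart clause is met while a trigger still applies, so the two rules conflict and the trigger bars dosing.

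**Smallest change that suffices.** After a joint trigger without jaundice and with A between 3 and 5, bilirubin falling from 2.1 to 2.0×ULN is enough: (2.1 − 2.0)/2.1 = 4.8%, with no fall in ALT/AST. In the other direction, once A ≤ 2 the clause sets no ceiling on bilirubin.

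**Distance from the apparently intended limit**, for a limit from just under 3×ULN down to 2×ULN:
- At A = 5: 5/3 = 1.7 to 5/2 = 2.5 times.
- At A = 8: 8/3 = 2.7 to 8/2 = 4 times. This needs A > 5 to have lasted 2 weeks or less.

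**Fall in ALT/AST that the limit would demand**, over the same range:
- From 8×ULN: (8 − 3)/8 = 62.5% to (8 − 2)/8 = 75%.
- From 5×ULN: (5 − 3)/5 = 40% to (5 − 2)/5 = 60%.
- From 3×ULN: (3 − 3)/3 = about 0% to (3 − 2)/3 = 33%.

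**Transaminase-only interruptions.** On the strictest literal reading, a bilirubin that was never above 2×ULN already meets the clause on the day dosing stops. It is then enough to leave the trigger: without jaundice, A falling from 8.1 to 8.0 (0.1/8.1 = 1.2%) if A > 5 has lasted 2 weeks or less, or from 5.1 to 5.0 (0.1/5.1 = 2.0%) after the 2-week trigger.

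**The case against.** The strongest reply is that the clause should be read with the words that open its sentence. Those list raised transaminases and/or raised bilirubin, so what must return is whatever was raised. 'Return' implies an earlier departure, and a reading under which the condition is met at the moment dosing must stop makes the 2×ULN limit pointless. This largely answers the transaminase-only case. A reader might infer that the rule in effect sets no transaminase limit whenever bilirubin was normal. The alternative 'or are' wording leaves room for that, but it is strained and probably not intended. The reply does not settle a joint trigger in which both analytes were raised, because 'or' still does not demand both. Nor does it bring jaundice into the condition.

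A reader might also infer that one recovered analyte is all that restart needs. It is not. An alternative, reversible cause must have been identified and the medical monitor told beforehand, though approval is not required. Resumption is permitted rather than required, and under 9.9 the investigator or sponsor may withdraw a subject for safety at any time.

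Finally, a subject never interrupted may keep dosing in some of the same states, such as ALT 4.5×ULN with bilirubin at or below 2×ULN and no jaundice, or isolated bilirubin above 2×ULN. That is true and limits the added risk. But the protocol sets its restart limit below its interruption limits, so it evidently means to ask more of a subject who has already been interrupted.

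**Conclusion.** The point holds as a wording defect in an individual-subject safety rule. As written, the recovery clause does not require every raised analyte to recover or jaundice to resolve, and the joint trigger is where this is clearest. The intent is probably sound, and the documents do not support reading the rule as deliberately lax.

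The ratios of 1.7 to 2.5 and 2.7 to 4 describe what the text permits at 5 and 8×ULN. They are not expected values, and they assume a baseline ALT/AST within the screening limit. The documents give no frequency for such events. With about 12 subjects in Part D, 9 of them on active drug for 4 weeks, an affected subject should be rare. The existing safeguards keep the practical risk small, and no endpoint or analysis depends on the clause. It is worth correcting because the correction is cheap.

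**What to change.** Replace the recovery clause in Protocol 9.8.2 with: *once ALT, AST and total bilirubin are each no higher than the greater of baseline and 2×ULN, and any clinical jaundice that was part of the interruption has resolved*. Keep the cause requirement, the notice to the medical monitor, the weekly tests and the rechallenge rule as they are.

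This changes one sentence, moves no numeric limit and adds no visit or test. It goes slightly beyond settling the ambiguity, since it makes resolution of jaundice an explicit condition. The cost is a possibly longer interruption for a rare subject, which in a 29-day course may lose some of that subject's on-treatment data.
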